9.1 DATA MANAGEMENT PLAN

A detailed Data Management Plan will be established to ensure consistency of the data. This document will include procedures used for data review, database cleaning, and issuing and resolving data queries. If appropriate, the DMP may be updated throughout the study duration. All revisions will be tracked and document controlled.

CRF data will be captured in a validated electronic database management system hosted by St. Jude Medical.

Only authorized site personnel will be permitted to enter the CRF data through the electronic data capture (EDC) system deployed by St. Jude Medical. An electronic audit trail will be used to track any subsequent changes of the entered data.

9.2 DOCUMENT AND DATA CONTROL

9.2.1 Traceability of documents and data

The investigator will ensure accuracy, completeness, legibility and timeliness of the data reported to the sponsor on the CRFs and in all required reports.

9.2.2 Recording data

Source documents will be created and maintained by the investigational site team throughout the clinical study.

The data reported on the CRFs will be derived from, and be consistent with, these source documents, and any discrepancies will be explained in writing.

No data can be recorded directly in the CRFs.

The CRFs will be validated (eCRF) by the authorized site personnel.

10.0 MONITORING

Monitoring will be conducted according to St. Jude Medical's Clinical Monitoring work instruction.

Prior to beginning the clinical investigation, the Sponsor will contact the investigator or designee to discuss the clinical investigation and data requirements. A designated monitor will periodically review the subject records and associated source documents. The investigator shall make subject and clinical investigation records available to the clinical monitor for monitoring.

Clinical Investigational Plan

11.0 REGULATORY INSPECTIONS

The investigator and/or delegate should contact St. Jude Medical immediately upon notification of a governmental agency inspection at the site. A clinical monitor or designee will assist the investigator and/or delegate in preparing for the audit.

An investigator who has authority to grant access will permit authorized governmental agency employees, at reasonable times and in reasonable manner, to enter and inspect any establishment where devices are held (including any establishment where devices are used or where records or results are kept).

An investigator, or any person acting on behalf of such a person with respect to the study, will permit authorized governmental agency employees, at reasonable times and in reasonable manner, to inspect and copy all records relating to the study.

[figure not shown]
An investigator will permit authorized governmental agency employees to inspect and copy records that identify subjects, upon notice that governmental agency has reason to suspect that adequate informed consent was not obtained, or that reports required to be submitted by the investigator, to the Sponsor or IRB/EC have not been submitted or are incomplete, inaccurate, false or misleading.

12.0 STATISTICAL CONSIDERATIONS

12.1 STATISTICAL DESIGN, HYPOTHESES, METHOD AND ANALYTICAL PROCEDURES

The primary endpoint is the proportion of subjects who indicate preference on constant current over constant voltage at the 3 Month follow-up visit.

12.1.1 Primary Endpoint

12.1.2 Secondary Endpoint

The rate of safety events related to battery replacement procedures for hybrid systems.

Clinical Investigational Plan

The event rate will be summarized as (1) # events per patient-year of follow up and (2) incidence rate. The number of events per patient-year of follow-up will be calculated as the total number of safety events related to battery replacement procedures for hybrid systems divided by total follow-up duration from IPG replacement visit to either 12M visit or withdrawal visit (patient-years). The incidence rate (%) will be calculated as number of subjects who undergo IPG replacement and encounter safety events related to battery replacement procedure for hybrid system divided by total subjects who undergo IPG replacement.

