1.0 SYNOPSIS

Title:	Prospective evaluation comparing the effects of constant current versus constant voltage in Deep Brain Stimulation using hybrid systems*.
Acronym:	PREFERENCE-H
Purpose:	To evaluate subject's preference for different stimulation modes (i.e. constant voltage and constant current).
Primary Objective:	The primary objective of the study is to demonstrate the subject's preference for a stimulation modality.
Secondary Objective:	The secondary objective of the study is to demonstrate the safety of the hybrid DBS system.
Primary Endpoint:	The primary endpoint is the proportion of subjects who indicate preference on constant current over constant voltage at the 3 Month follow-up visit.
Secondary Endpoint:	The secondary endpoint is the rate of safety events related to battery replacement procedures for hybrid systems.
Descriptive Endpoints:	
• The change in Speech Handicap Index at 3 and 12 Months compared to Baseline;• The change in total UPDRS score and the individual UPDRS components at 3 and 12 Months compared to Baseline;• The change in Levodopa medication at 3 and 12 Months compared to Baseline;• The change in Freezing of Gait Questionnaire (FOGQ) scores at 3 and 12 Months compared to Baseline;• The change in Tinetti Test scores at 3 and 12 Months compared to Baseline;• The change in Berg Balance Scale scores at 3 and 12 Months compared to Baseline;• The change in PDQ-39 scores at 3 and 12 Months compared to Baseline;• Proportion of subjects who indicate satisfaction with constant current at 3 and 12 Months;• Proportion of caregivers who indicate satisfaction with constant current at 3 and 12 Months;• Proportion of subjects who indicate preference on the constant current over the constant voltage at the 12 Month follow-up visit;• Summary of Health Economic Data for constant current compared to constant voltage.
Design:	Prospective, multicenter, multinational, post-market clinical study. The clinical study will be conducted in approximately 20 centers in Europe, Australia and the United States and approx. 170 subjects will be enrolled. Subjects will be followed for 12 months post battery replacement. The total duration of the study for a subject is expected to be approximately 15-24 months.

Clinical Investigational Plan

Devices used:	
• St Jude Medical Infinity™ DBS system• St Jude Medical Brio™ DBS system

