The targeted study population consists of subjects who have been previously implanted with a Medtronic® DBS device and re-implanted at the IPG's end of life with a St Jude Medical Infinity™ DBS or St Jude Medical Brio™ DBS constant current system. Subject's preference will be collected for the 2 stimulation modes (i.e. constant voltage and constant current).

Effects of the DBS with constant current as well as with a constant voltage device are considered safe, non-destructive and reversible. The frequency and severity of procedural risks and complications related to the replacement of a Medtronic® device (constant voltage or constant current) by an Infinity™ device or Brio™ device (constant current) are expected to be similar to those cited in the current literature.

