6.5 IPG REPLACEMENT VISIT & PROGRAMMING

The implanted Medtronic® IPG will be explanted and replaced by a SJM Infinity™ DBS IPG or a SJM Brio™ DBS system according to the standard surgical procedures and instructions for use. The time point for the replacement will be decided by the physician according to their standard procedure.

Intra-operative assessments and the initial CC programming session will be performed according to each individual site's standard procedure.

The frequency, pulse width and number of contacts (monopolar/bipolar) of the stimulation should be kept constant between the constant voltage and the constant current stimulation.

Additional programming sessions may be required to optimize the therapy.

The following data will be collected:

- Implant information
- Initial programming information
- Adverse Events or Withdrawal (if applicable)

6.6 3 MONTH FOLLOW UP VISIT (3 months +/- 30 days after IPG replacement)

The current programming settings will be recorded before the questionnaires and tests.

The following data will be collected:

- Subject's Preference
- Speech Handicap Index (SHI)
- Unified Parkinson's Disease Rating Scale 'On Med/On Stim' ("On" state is defined as approximately 30 minutes after a subject takes anti-Parkinson medication when both the clinician and the subject indicate that the medication dose is effective.)
- Unified Parkinson's Disease Rating Scale part III 'On Med/Off Stim'
- Freezing of Gait Questionnaire (FOGQ)
- Tinetti Test
- Berg Balance Scale (BBS)
- Parkinson's Disease Questionnaire (PDQ-39)
- Satisfaction of Therapy Questionnaire for the subject
- Satisfaction of Therapy Questionnaire for the caregiver, if applicable
- Medication
- Adverse events or Withdrawal (if applicable)

After the questionnaires and the tests, the SJM Infinity™ or Brio™ DBS system parameters shall be optimized if needed. The optimized settings will be recorded.

6.7 12 MONTH FOLLOW UP VISIT (12 months +/- 30 days after IPG replacement)

This visit will also serve as the end-of-study assessment.

The current programming settings will be recorded before the questionnaires and tests.

Clinical Investigational Plan

The following data will be collected:

- Subject's Preference
- Unified Parkinson's Disease Rating Scale 'On Med/On Stim' ("On" state is defined as approximately 30 minutes after a subject takes anti-Parkinson medication when both the clinician and the subject indicate that the medication dose is effective.)

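### Section 12.1.2 should report replacement-procedure safety as cumulative incidence at stated times: the patient-year rate moves with withdrawal, and the percentage has only an implicit horizon.

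*Combined protocol and SAP*

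**What the plan says.** The secondary objective (section 4.3.2) is to show that the hybrid system is safe. Its only endpoint (section 4.4.2) is the rate of safety events related to battery replacement. Section 12.1.2 states: "The event rate will be summarized as (1) # events per patient-year of follow up and (2) incidence rate".

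- **Statistic (1)** is the "total number of safety events related to battery replacement procedures for hybrid systems divided by total follow-up duration from IPG replacement visit" to the 12-month or the withdrawal visit, in patient-years.
- **Statistic (2)** is described thus: "The incidence rate (%) will be calculated as number of subjects who undergo IPG replacement and encounter safety events related to battery replacement procedure", and this number is "divided by total subjects who undergo IPG replacement".

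No time window is written beside the percentage, and no confidence interval, hypothesis or margin is given in section 12.1.2.

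The horizon has to be pieced together from other sections. The synopsis says: "Subjects will be followed for 12 months post battery replacement". Section 6.7 allows 30 days either side of the 12-month visit. Section 8.2 runs safety surveillance to the last visit, death, or the end of participation.

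Section 12.6 restricts each endpoint's analysis to subjects with complete data and plans no imputation. Section 3.4 says that the frequency and severity of procedural risks "are expected to be similar to those cited in the current literature", without a figure or a time base.

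**The concern.** The exposure here is one operation. Events per patient-year describe risk well when the rate is roughly constant over time. If procedure-related events fall mainly soon after surgery, later event-free time adds to the denominator and says little about the operation. The figure then depends on how long subjects stay.

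The percentage has a different weakness. A subject who withdraws without an event remains in the denominator as event-free, although related events after withdrawal would not be seen. Section 3.3 lists erosion over the generator, persistent pain and impaired wound healing without saying when they occur, so late related events cannot be ruled out.

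Withdrawal may also be tied to the operation: section 6.12 names unplanned lead or extension revision during replacement as a reason for it.

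At stake is how clearly the study's only formal safety endpoint can be read, and how well it can be compared with published risks that have a stated time base.

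**Working it through.** The plan gives no expected safety rate or precision target, so there is no figure of its own to reproduce. The inputs below marked as assumed are not in the documents.

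**Statistic (1), effect of withdrawal.** Assumed: 140 subjects replaced, 10 early events (one per subject), and 20% leaving at 3 months.
- Full 12 months: 10 / 140 = 0.071 per patient-year.
- With withdrawal: patient-years = 140 × (0.8 × 1 + 0.2 × 0.25) = 119, and 10 / 119 = 0.084. That is 140/119 = 1.18 times the first figure, with the same surgical outcome.

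**Statistic (1), effect of follow-up length.** Formula: p / [((1 − w) × T + w × t) / 12], where p is the risk per replacement, T is follow-up in months, and w is the share leaving at month t. Assumed p = 5%, all events early:

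| Follow-up | Per patient-year |
|---|---|
| 11 months, none leave | 0.055 |
| 12 months, none leave | 0.050 |
| 13 months, none leave | 0.046 |
| 12 months, 10% leave at month 3 | 0.054 |
| 12 months, 32.4% leave at month 3 | 0.066 |
| 12 months, 32.4% leave at month 1 | 0.071 |

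The visit window alone (about 11 to 13 months) moves it by roughly +9% to −8%. The heaviest assumed withdrawal moves it by +42%. The 32.4% is 1 − 115/170, from the two targets in section 12.2. The plan does not call this a dropout rate, and part of the gap may be subjects never replaced, so it serves here as a heavy case.

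**Statistic (2), early events only.** In the 140-subject example it is 10 / 140 = 7.1% with or without withdrawal. Kaplan-Meier gives the same 7.1%, because every event precedes the first withdrawal.

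**Statistic (2), with late events.** Assumed: 5% risk in month 1, then a related-event hazard of 0.05 per patient-year. Risk by month m is 1 − 0.95 × exp(−0.05 × (m − 1)/12).
- Month 3: 5.8%. Month 12: 9.3%.
- Crude percentage with 32.4% leaving at month 3: 0.676 × 9.3% + 0.324 × 5.8% = 8.1% (unrounded inputs 9.26% and 5.79%).
- With a late hazard of 0.02 the pair is 6.3% against 6.7%.

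If withdrawal is unrelated to risk, censoring at withdrawal recovers the full-follow-up value: 0.942 (event-free at month 3) × exp(−0.05 × 9/12) = 0.942 × 0.963 = 0.907, so 9.3%.

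**Precision.** Exact 95% intervals near an assumed 5% risk are 6/115 = 5.2% (1.9% to 11.0%) and 8/170 = 4.7% (2.1% to 9.1%).

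**The case against.** The best defence is that the plan already contains the right kind of figure. Statistic (2) counts replaced subjects in its denominator, so it is a per-replacement risk, and it is unaffected when all events are early and observed. Its horizon is not truly missing: 12-month follow-up, surveillance to the last visit and the end-point of statistic (1) together imply about 12 months. With complete 12-month follow-up, statistic (1) equals events per replacement (0.071 beside 7.1%), so it does not understate them. Under section 6.12 a subject withdrawn for an adverse event is followed until that event resolves or stabilises, so only new related events after withdrawal are lost. The documents say nothing about event timing. If events are early, only statistic (1) is clearly affected; the weakness of statistic (2) needs late events. No hypothesis or margin in section 12.1.2 rests on either statistic.

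All of this stands, and it limits the point. It does not supply a written horizon, a rule for subjects who leave before it, or a measure of uncertainty. Nor does it settle which rule governs: section 12.1.2 counts time up to withdrawal, while the complete-data rule in section 12.6 could be read as removing those subjects.

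**Conclusion.** The point holds in a limited form. Statistic (1) is a poor main summary for a one-time procedure: at unchanged risk it rises from 0.071 to 0.084 in the 140-subject example. Statistic (2) is sound if related events are early. It falls short by about 1.1 percentage points (8.1% against 9.3%) under heavy withdrawal and the larger assumed late hazard, and by about 0.5 points (6.27% against 6.73%) with the smaller one. Event timing, numbers of events and withdrawal rates are all assumptions.

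A reader might infer that the reported safety depends on follow-up length instead of on the risk of the replacement, or that neither statistic can be compared with the literature. The documents do not support either reading. The percentage is a per-replacement risk and could be set roughly against a published 12-month percentage. A reader might also compare the year-average rate with a rate over an assumed short risk window and see a large dilution; that ratio only restates the window chosen. What remains is a worthwhile, inexpensive improvement to the study's only formal safety endpoint.

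**What to change.** In section 12.1.2:

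- Make the main safety figure the cumulative incidence of first procedure-related event per replaced subject at prespecified times after replacement, for example one early time point and 12 months. The documents name no early time point, so the sponsor should choose and justify one before analysis.
- Estimate it by Kaplan-Meier, or Aalen-Johansen with death as a competing event. Censor at withdrawal, and give a 95% confidence interval and numbers at risk.
- Keep events per patient-year as a supplement, split into an early and a later period.
- State that section 12.1.2, which counts time to withdrawal, governs this endpoint and not the complete-data rule in section 12.6. Also state the end-of-follow-up date for subjects who die, are lost or miss the 12-month visit.
- Tabulate withdrawals by reason and time, because censoring does not remove bias if withdrawal is related to risk.

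The cost is analysis wording, event onset and end-of-follow-up dates in the analysis file, and a little more analysis work. The figures may look slightly less favourable than those now planned.

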12.1.3 Descriptive Endpoints

The following descriptive endpoints will be reported:

- The change in Speech Handicap Index at 3 and 12 Months compared to Baseline;
- The change in total UPDRS score and the individual UPDRS components at 3 and 12 Months compared to Baseline;
- The change in Levodopa medication at 3 and 12 Months compared to Baseline;
- The change in FOGQ scores at 3 and 12 Months compared to Baseline;
- The change in Tinetti Test scores at 3 and 12 Months compared to Baseline;
- The change in Berg Balance Scale scores at 3 and 12 Months compared to Baseline;
- The change in PDQ-39 Quality of Life scores 3 and 12 Months compared to Baseline;
- Proportion of subjects who indicate satisfaction with constant current at 3 and 12 Months;
- Proportion of caregivers who indicate satisfaction with constant current at 3 and 12 Months;
- Proportion of subjects who indicate preference on constant current over constant voltage at the 12 Month follow-up visit.
- Summary of Health Economic Data for constant current compared to constant voltage.

12.2 SAMPLE SIZE

The target number of subjects for enrollment is 170 and the target number of subjects for the primary endpoint analysis is 115.

12.3 PROCEDURES FOR REPORTING ANY DEVIATION(S) FROM THE ORIGINAL STATISTICAL PLAN

Any deviation from the statistical plan will be documented and reported.

12.4 THE SPECIFICATION OF SUBGROUPS FOR ANALYSIS

No subgroup analyses are planned for this study.

12.5 PROCEDURES THAT TAKE INTO ACCOUNT ALL THE DATA

All reported data will be used in the analysis for relevant endpoints. Missing data will be excluded from the respective endpoint analysis.

Clinical Investigational Plan

12.6 THE TREATMENT OF MISSING, UNUSED, OR SPURIOUS DATA, INCLUDING DROP-OUTS AND WITHDRAWALS

Analyses of each endpoint will be performed in subjects who provide complete data for each endpoint. Subject accountability for enrolled subjects will be performed prior to analyses of the primary and secondary endpoints. There are no plans to perform imputations for missing data, subject dropouts or withdrawals. If spurious data are discovered, these data will be excluded from analyses. Reasons for exclusion of any data from analyses will be summarized.

12.7 THE EXCLUSION OF PARTICULAR INFORMATION FOR THE TESTING OF THE HYPOTHESIS, if relevant

There is no intent to exclude particular information for the testing of hypotheses.

12.8 IN MULTI-CENTER STUDIES, THE MINIMUM AND MAXIMUM NUMBER OF SUBJECTS TO BE INCLUDED FOR EACH CENTER

Each participating will enroll at least one subject to a maximum of 30 subjects.

13.0 DOCUMENT RETENTION

St. Jude Medical and the Principal Investigators will maintain the clinical study documents as required by St. Jude Medical, Inc. and applicable regulatory requirements. They will take measures to prevent accidental or premature destruction of these documents. The Principal Investigator or St. Jude Medical may transfer custody of records to another person/party and document the transfer at the investigational site or at St. Jude Medical's facility.

These documents must be retained by the investigational site for a minimum period of 2 years after clinical study conclusion and made available for monitoring or auditing by St. Jude Medical's representative or representatives of the FDA and other applicable regulatory agencies. The Principal Investigator must ensure the availability of source documents from which the information on the case report forms was derived.

14.0 AMENDMENTS TO CLINICAL INVESTIGATIONAL PLAN

Study related documents such as, the Investigator Brochure (IB), Report of Prior Investigations (RPI) CIP, CRFs, Informed Consent form and other subject information, or other clinical study documents will be amended as needed throughout the clinical study, and a justification statement will be included with each amended section of a document. Proposed amendments to the CIP will be agreed upon between the Sponsor and the coordinating investigator (if applicable).

The amendments to the CIP and the subject's Informed Consent will be notified to, or approved by, the IRB/EC and regulatory authorities, if required. The version number and date of amendments will be documented.

Clinical Investigational Plan

The amendment will identify the changes made, the reason for the changes and if it is mandatory or optional to implement the amendment.

Any amendment affecting the subject requires that the subject be informed of the changes and a new consent be signed and dated by the investigator at the subject's next follow up.

Changes to, or formal clarifications of, the CIP will be documented in writing and provided to the investigators. This information will be incorporated when an amendment occurs.

15.0 INVESTIGATION SUSPENSION OR TERMINATION

15.1 PREMATURE TERMINATION OF THE WHOLE CLINICAL STUDY OR OF THE CLINICAL STUDY IN ONE OR MORE INVESTIGATIONAL SITES

The Sponsor reserves the right to stop the study at any stage, with appropriate written notice to the investigator.

Possible reasons for early termination of the study by the sponsor, either at local, national or international level, may include, but are not limited to:

- The subject needs an unplanned revision of the lead and/or extension during the IPG replacement
- The device / therapy fails to perform as intended
- Occurrence of USADE which cannot be prevented in future cases
- Sponsor's decision
- Recommendation from DSMB to Steering committee and Sponsor
- Request from Regulatory bodies
- Request of Ethics Committee(s)
- Concern for subject safety and welfare
- Failure to secure subject Informed Consent prior to any investigational activity
- Repeated non-compliance with this CIP or the Clinical Trial Agreement
- Inability to successfully implement this CIP
- Violation of the current Declaration of Helsinki
- Violation of applicable national or local laws and regulations
- Falsification of data, or any other breach of ethics or scientific principles
- Loss of or unaccounted use of investigational device inventory

The study will be terminated according to applicable regulations.

The investigator may also discontinue participation in the clinical study with appropriate written notice to the Sponsor.

Should either of these events occur, the investigator will return all documents to the sponsor; provide a written statement as to why the premature termination has taken place and notify the IRB/EC and/or the Competent Authority (if applicable). Follow-up for all enrolled subjects will be as per CIP requirements.

A Principal Investigator, IRB/EC or regulatory authority may suspend or prematurely terminate participation in a clinical study at the investigational sites for which they are responsible.

Clinical Investigational Plan

If suspicion of an unacceptable risk to subjects arises during the clinical study or when so instructed by the IRB/EC or regulatory authority, St. Jude Medical may suspend the clinical study as appropriate while the risk is assessed. St. Jude Medical will terminate the clinical study if an unacceptable risk is confirmed.

St. Jude Medical will consider terminating or suspending the participation of a particular investigational site or investigator in the clinical study if monitoring or auditing identifies serious or repeated deviations on the part of an investigator.

If suspension or premature termination occurs, the terminating party will justify its decision in writing and promptly inform the other parties with whom they are in direct communication. The Principal Investigator and St. Jude Medical will keep each other informed of any communication received from IRB/EC or regulatory authority.

If for any reason St. Jude Medical suspends or prematurely terminates the study at an individual investigational site, St. Jude Medical will inform the responsible regulatory authority, as appropriate, and ensure that the IRB/EC are notified, either by the Principal Investigator or by St. Jude Medical. If the suspension or premature termination was in the interest of safety, St. Jude Medical will inform all other Principal Investigators.

If suspension or premature termination occurs, St. Jude Medical will remain responsible for providing resources to fulfill the obligations from the CIP and existing agreements for following up the subjects enrolled in the clinical study, and the Principal Investigator or authorized designee will promptly inform the enrolled subjects at his/her investigational site, if appropriate.

